8.6.1 Selecting Family Meetings

Working with several CICU team members, we will identify family meetings that are scheduled. We will confirm with the primary team planning the family meeting which family members are likely to be present and we will contact them either via phone, in person or via e-mail to discuss the study. We will also confirm with the primary team who the other clinicians are that are likely to be present in the meeting and we will contact them either via email or in person to discuss the study.

When audio or video recording participating clinicians during actual family meetings, others present at the meeting will be recorded as well. This will include parents, patients, and

clinician team members participating in an observed family meeting who did not undergo the CST (because they were not eligible, did not wish to participate in the study, or were not approached because sufficient clinicians were already enrolled).

Parent-Patient Dyads Prior to the Intervention

During recruitment within the CICU in-patient units, a member of the research team will approach parents and patients who will be participating in an observed family meeting in the patient room, or over the phone if the parents will not be in the CICU prior to the family meeting and provide information about the study. A member of the study team will present a one-page explanation of the study to the parents. The explanation will cover the purpose of the study, procedures, risks and benefits of participation, what information will be collected, contact information for study personnel, that their private information will not be written down or used, and that parents can opt-out at any time.

Patients who are 18 years old and will be present in the audio recorded family meeting will be allowed to opt-out as adults if they are medically and cognitively capable of comprehending study purposes and can decline participation.

Parent-Patient Dyads After the Intervention

During recruitment within the CICU in-patient units, a member of the research team will approach parents and patients who will be participating in an observed family meeting in the patient room, or over the phone, or via email if the parents will not be in the CICU prior to the family meeting and provide information about the study. A member of the study team will consent the parents prior to study procedures would begin. The explanation will cover the purpose of the study, procedures, risks and benefits of participation, what information will be collected, contact information for study personnel, that their private information will not be written down or used, and that parents can opt-out at any time.

Patients who are 18 years old and will be present in the audio or video recorded family meeting will be allowed to opt-out as adults if they are medically and cognitively capable of comprehending study purposes and can decline participation.

8.7 Payment to Subjects/Families

Clinicians and parents participating in the co-design will be given \$25 per hour session, totaling \$275 for all 11 sessions in the form of a debit card or gift card. Clinicians participating in the intervention will be given \$100 for the entirety of the intervention participation. Parent subjects will be given \$10 in the form of a debit card or gift card upon completion of either the survey or the interview in the pre-intervention. Parent subjects will be given \$20 in form of a debit card or gift card upon completion of the survey or the interview in the post-intervention. Patient subjects will not receive any payment for their participation.

9 PUBLICATION

We aim to publish findings of this study in peer-reviewed articles in leading medical journals. We will also present findings at professional meetings.

## Statistical Analysis Plan

Aim 2: Pilot test the co-design-adapted CICU TALC with CICU parents and clinicians to determine:

a) Acceptability of intervention: Hypothesis: Respondents will endorse above a critical threshold of acceptability on satisfaction instruments to 20 clinicians and 23 parents and in semi-structured interviews.

Analytic plan: A constructivist grounded theory approach will guide qualitative analysis of interview transcripts regarding acceptability of the intervention. Descriptive statistics will be calculated for quantitative data from the acceptability survey.

b) Feasibility of enrollment and data collection, and fidelity: Hypothesis: Feasibility will be defined by: i) 30% parental and 50% clinician enrollment and consent rates, and 80% subject retention, and attrition; ii) ability to collect outcomes data from 46 patients (CICU length of stay), from 46 parents and from 50% of eligible team members. and iii) intervention fidelity with 95% of enrolled parents and clinicians receiving parent-directed and team-directed interventions.

Analytic Plan: Data completeness and accuracy will be monitored. I will calculate descriptive summaries including means and standard deviations for continuous variables, and proportions for categorical variables. As appropriate for pilot trials, analyses will focus on estimating proportions of binary feasibility and fidelity endpoints and constructing 95% CIs. Analyses of parent-reported outcomes will primarily be descriptive. Means and standard deviations along with 95% confidence intervals will be calculated.

c) Impact of CICU TALC on CICU parent and team behavior in family meetings. Hypothesis: the intervention will increase parent speaking time by 60%, elicitation of parental concerns to 40%, and response to parental emotion by 30%. I will audio record 230 CICU family meetings occurring before CICU TALC is initiated and 230 after initiation and use quantitative methods to measure pre-vs-post differences in a) speaking time of parents and physicians; b) elicitation of parental concerns; and c) response to parental emotion.

Analytic Plan:

- Speaking time will be analyzed by comparing the change in the number of words spoken by physicians versus parents speak in pre- and post-CICU TALC meetings using generalized linear regression with binomial link function controlling for the length of the meetings. Means and standard deviations will be calculated for the tool and t-tests will determine if significant differences exist for the two groups pre and post-CICU TALC.
- Elicitation of parental concerns and empathic response to parental emotion will be determined through quantitative coding. Each skill will be analyzed separately, using the cutoffs to identify skill proficiency as used by Back. Univariate relationship pre/post intervention by outcomes (Table 1)
  - If the outcomes (skills acquisition scores) are continuous and satisfies the normality assumptions, then t-tests will be appropriate to compare pre – intervention and post – intervention changes.

- If outcomes are continuous but not normally distributed, then a Wilcoxon Rank sum test will be appropriate to compare pre –intervention and post –intervention changes.
- If outcomes are binary (high vs low), then chi-square/fishers exact tests will be appropriate to compare pre –intervention and post –intervention changes.
- Similar statistical analysis will be performed to compare pre –intervention and post –intervention changes overall and for each type of participant.
- Analyses will be presented at the meeting-level as well as the participant-meeting level. Participant-meeting level data will be stratified by physician-type pending  $\geq 5$  participants in the pre- and post-intervention groups for each type.
- Relationship pre/post intervention by outcomes adjusted for participant and meeting level characteristics
  - If sample size allows and there are significant univariate associations, we will utilize mixed effect regression models to explore the relationship between the intervention and outcomes, first controlling for--gender and years of experience and accounting for correlation of repeated measurements within participants. If sample size allows, we will include other characteristics including number of participants at the meeting, proportion of speaking time by participant type, etc

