Potential subjects will be screened using the protocol inclusion and exclusion criteria. Parent-patient dyads will be recruited into the study in person, over the phone, or via e-mail. The goal for enrollment will be up to 50 parent-patient dyads, with 30 evaluable parent-patient dyads. Parent-patient dyads who are enrolled in the post-intervention follow-up phase will be asked for access to information entered into the REDCap based Family Meeting Worksheet if they choose to use it, will be given an online survey in person or via e-mail to obtain post-intervention data assessing parental satisfaction, understanding, trust in the clinical team, emotional well-being and parents' acceptability of the parent-facing elements of the intervention, which includes preparation for the meeting and their perception of the written summary after the family meeting. Medical record review of this group of parents will utilize EPIC and the PC⁴ database, but will not require patient or parent involvement. A subset of enrolled patient-parent dyads will also be invited to participate in an interview assessing parents' acceptability of the parent-facing elements of the intervention.

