3.3.2 Total Number of Study Sites/Total Number of Subjects Projected

The study will be conducted within the Children's Hospital of Philadelphia. The co-design phase will be conducted with participants from units within the hospital and parents with children who had previously been hospitalized at CHOP, and the intervention and evaluation of the intervention will occur exclusively in the CICU at CHOP.

For clinicians participating in the co-design, approximately 15 clinician staff will be enrolled and 5 parents will be enrolled.

For clinician subjects participating in the intervention, recruitment will stop when at least 20 CICU clinicians are enrolled.

For non-participating clinicians, recruitment will stop when we obtain at least 56 family meetings per discipline of participating clinician team member.

We estimate that approximately 300 clinicians who are not participating in the intervention may be observed subjects in the actual meetings.

For parent-patient dyads participating prior to the intervention, recruitment will stop when 100 evaluable parent-patient dyads are enrolled for the survey and 30 evaluable parent-patient dyads are enrolled for the interview.

For parent-patient dyads participating after the intervention, recruitment will stop when up to 30 evaluable parent-patient dyads are enrolled for the survey and a subset of up to 15 parent-patient dyads will be asked to participate in the interview.

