A sample size of 130 parent-patient dyads for the survey and 30 parent-patient dyads for the interview is based on using CONSORT recommendations for pilot study sample size calculations. We calculated the parent-patient dyad sample size by estimating the required sample size for the future stepped wedge study using the Hospital Anxiety and Depression Scale (HADS) as the primary outcome for parents, as HADS is a frequently used outcome in palliative care research with well-established psychometric properties.^{129,130} We will assume a one sided 80% CI for the effect size of 0.1 times the SD, to exclude the minimum clinically important difference if the null hypothesis is true.¹³¹ The minimally important difference is a change of 2 on the HADS scale. The estimated sample size for the main study would be 286. For the pilot study, we estimated the number of participants required as around 30% of the number required for the main Phase 3 trial therefore, we aim to enroll a total of 46 parent-patient dyads pre and post the intervention. In previous studies enrolling parents and children with serious illness, our approach-to-enrollment rate was above 50%. Assuming 45% or more of parent-patient dyads approached will enroll and there are 150 eligible patients per year, we will need to approach approximately 350 parent-patient dyads to enroll 130 evaluable parent-patient dyads for the survey and 30 evaluable parent-patient dyads for the interview prior to the intervention. We have allotted 24 months to enroll 46 evaluable parent-patient dyads for the survey and 20 evaluable parent-patient dyads for the interview pre-intervention.

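### The SAP's feasibility count of 46 patients and 46 parents names no phase, does not follow from its derivation, and can be met with no post-intervention outcome data

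*SAP*

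**What the plan says.** SAP Aim 2b defines feasibility by three criteria. The second, on data collection, is "ability to collect outcomes data from 46 patients (CICU length of stay), from 46 parents and from 50% of eligible team members". It names no study phase.

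Protocol 6.4 is the only place that explains 46, and it gives several figures in one paragraph:

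- It opens with "A sample size of 130 parent-patient dyads for the survey and 30 parent-patient dyads for the interview".
- It puts the main study at 286 and says "we estimated the number of participants required as around 30% of the number required for the main Phase 3 trial". From this it concludes "we aim to enroll a total of 46 parent-patient dyads pre and post the intervention".
- It plans to "approach approximately 350 parent-patient dyads to enroll 130 evaluable parent-patient dyads for the survey", together with 30 for the interview, assuming that 45% or more of those approached enrol.
- It closes with "We have allotted 24 months to enroll 46 evaluable parent-patient dyads for the survey and 20 evaluable parent-patient dyads for the interview pre-intervention".

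The recruitment targets stand elsewhere. Before the intervention, Protocol 3.3.2 says "recruitment will stop when 100 evaluable parent-patient dyads are enrolled for the survey", and Protocol 8.5 expects 95 evaluable from up to 100 enrolled. After the intervention, Protocol 3.1 says "The goal for enrollment will be up to 50 parent-patient dyads, with 30 evaluable parent-patient dyads", and Protocol 3.3.2 and 8.5 repeat the 30. Protocol 6.2 gives 37 dyads for most of the pre-intervention parent scales. SAP Aim 2a gives 23 parents for the satisfaction instruments.

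**The concern.** Criterion ii is the only one of the three that sets a number for collecting patient and parent outcome data. Only post-intervention parents receive the preparation worksheet and the written summary, so collecting outcomes while those elements are in use is the part that most needs testing. Protocol 6.4 sizes the parent sample with a future stepped-wedge study in mind, with parental HADS as its primary outcome.

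A count that pre-intervention dyads can reach alone says nothing about that. The patient count has the same gap: CICU length of stay comes from record review, which also covers the pre-intervention survey dyads (Protocol 3.1 and 5.1.1). The number itself is also in doubt, because it matches neither its stated derivation nor the current recruitment targets.

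**Working it through.** **1. Reproducing 46.** Inputs from Protocol 6.4: main study 286, pilot fraction about 30%.

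- 0.30 × 286 = 85.8, or 86.
- 46 / 286 = 16.1%.
- 46 / 0.30 = 153.3, so 46 would be 30% of a main study of about 153.

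The stated rule does not give 46. Two other routes were tried.

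- Confidence-interval rule in the same paragraph (one-sided 80%, 0.1 SD), taken as two equal groups: N = 4 × (z₀.₈₀ / d)². With d = 0.1 this is 283.3, close to 286. It gives 45.3 only at d = 0.25, a value that is not in the documents.
- 23 + 23 = 46, using the 23 parents of SAP Aim 2a. The arithmetic matches, but no section states an equal split by phase.

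**2. Which figures the approach count uses.** At 45% enrolment:

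- (130 + 30) / 0.45 = 355.6, close to the stated 350 or so (350 × 0.45 = 157.5, against 160).
- (46 + 20) / 0.45 = 146.7.

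The count was built on 130 and 30, not on 46 and 20. It does not settle the phase split. 130 equals 100 + 30 from Protocol 3.3.2, but the sentence can also be read as placing all 130 before the intervention.

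**3. Setting 46 against the planned evaluable dyads.**

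| Meaning of 46 | Stated in | Planned evaluable | Post-intervention dyads needed |
|---|---|---|---|
| Total over both phases | Protocol 6.4 | 95 or 100 before, 30 after | 0 |
| Pre-intervention only | Protocol 6.4 | 95 or 100 | 0 |
| Total, if 37 were the true pre-intervention number | Protocol 6.4 with 6.2 | 37 before, 30 after | 46 − 37 = 9 |
| Post-intervention only | nowhere | 30, from up to 50 enrolled | 46, which is 16 more than planned |

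In the first two rows, 46 is reached with 46/100 = 46% or 46/95 = 48% of the pre-intervention dyads. If all 130 were pre-intervention, the margin would be larger still.

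In the last row, 46/50 = 92% of the enrolment ceiling would have to be evaluable, whereas the plan's own goal is 30/50 = 60%. If each of 50 enrolled dyads gave data independently with an assumed probability of 0.80, 0.90 or 0.95, the chance of at least 46 would be 0.018, 0.43 or 0.90.

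**4. Would correcting the arithmetic be enough?** No. The corrected 86 is also below 95 and 100, so pre-intervention dyads would still meet it alone. As a post-intervention count it would exceed the ceiling of 50. The phase has to be stated whatever the number.

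**The case against.** **Feasibility as a whole does cover the post-intervention phase.** This stands, and it limits the point. Criterion iii asks that 95% of enrolled parents and clinicians receive their parts of the intervention. Its denominator is stated, and for parents it can only mean post-intervention dyads. Its assessment also uses post-intervention parent data: Protocol 6.2 scores the fidelity checklist partly from parents' survey answers, and Protocol 5.1.1 asks parents whether they were given the worksheet. A reader might infer that the whole feasibility claim leaves out the phase in which the intervention is delivered, or that the fidelity criterion lacks a denominator. The documents support neither. What remains is that criterion iii concerns delivery and sets no count of outcome data.

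**The SAP does name a post-intervention parent number, the 23 of Aim 2a.** In part. Acceptability of the parent-facing elements is measured only after the intervention. But that 23 concerns satisfaction instruments, not the outcomes in criterion ii, and it differs from the goal of 30.

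**On the 37 of Protocol 6.2, pre-intervention dyads would not be enough.** Correct, if 37 were current. Protocol 3.1, 3.1.1, 3.3.2 and 8.5 all point to 95 to 100, although 3.1.1 and 8.5 word 100 as an upper limit.

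**A minimum below the recruitment target is not an error.** Agreed. That 46 is 35% of 130 proves little by itself. The fault lies in the missing phase and the failed derivation.

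**Aim 2 pilots the intervention, so 46 must be post-intervention.** No section says so, Protocol 6.4 attaches 46 to the pre-intervention phase, and Protocol 6.2 lists the pre-intervention parent scales as secondary endpoints. On that reading 46 would also exceed the recruitment stop of 30.

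**Nothing hangs on 46.** No section makes it a go/no-go rule. The SAP estimates feasibility and fidelity proportions with 95% confidence intervals, and Protocol 6.2 tracks missing data, though without a threshold. This lowers the stakes but leaves the criterion unclear.

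**Conclusion.** Criterion ii is wrong as written. It names no phase, and 46 is 16% of 286 where its stated rule gives 86. On both uses of 46 in Protocol 6.4, the 95 to 100 planned pre-intervention dyads satisfy it with no post-intervention outcome data. On the unstated post-intervention reading it asks for 16 more evaluable dyads than the plan recruits. So it needs correction on every reading.

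The conclusion that no post-intervention data are needed assumes that 95 to 100, not 37, is the current pre-intervention number; with 37, 9 post-intervention dyads would be needed. The consequence is confined to criterion ii: it could be reported as met without showing that patient and parent outcomes can be collected while the intervention is in use.

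**What to change.** - State criterion ii separately for the pre- and post-intervention phases, with the post-intervention threshold consistent with the goal of 30 evaluable dyads.
- In Protocol 6.4, correct or remove the derivation of 46 as about 30% of 286, and say once which phase or phases each target covers.
- Reconcile to one set of targets: 23 (SAP Aim 2a), 37 (Protocol 6.2), 46 (Protocol 6.4 and SAP Aim 2b), 95 (Protocol 8.5), 100 (Protocol 3.3.2) and 130 (Protocol 6.4).

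The retention and fidelity criteria need no change for this point. The cost is wording in the SAP and protocol, with no new data. The reported feasibility result may be less favourable once the post-intervention phase has its own threshold.
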